Statistical Procedures: This will be a prospective randomized double blind clinical trial. The primary outcome of the trial will be the incidence of PDPH at 48 hours after ADP. A study by Al-Metwalli et al. 2008 (4), utilizing 2 doses of epidural morphine, reported a PDPH headache rate of 12 % in the treatment arm and 48% in the saline arm. Estimates of PDPH rate after ADP range from 50 - 85%. Our internal QA data indicates our PDPH headache rate after an ADP with an epidural needle over the past several years is ~66%. We will consider a difference in incidence of PDPH between the placebo and treatment groups of 25% to be significant, based on the findings of Al Metwalli et al. (4) and the meta-analysis by Heesen et al. (3). For calculation of our sample size, we determined that an absolute 25% decrease in PDPH would be clinically significant (i.e., 66% - 40%). For a power of 90% and an alpha of 0.05%, this requires 83 subjects per group (2 epidural groups compared to each other, 2 spinal groups compared to each other). We are not specifically powering this for comparison of the spinal to the epidural groups, although we will likely be able to do so. We therefore aim to recruit 100 subjects per group (for a total of 400 across all centers) assuming 10- 15% of subjects may be lost because of inadvertent withdrawal of the catheter, subject withdrawal or loss to follow up after discharge. This is intended to be a multicenter study involving 5 or more academic tertiary-care hospitals, having >2,000 vaginal deliveries per year. Since the rate of accidental dural puncture is between 1 and 2%, we estimate we should be able to recruit 100 patients per year. Categorical data (presence of absence of PDPH, need for EBP) will be analyzed using Chi-square analysis. The

two main campuses of NYP will be included (CUMC (including Allen) and Weill-Cornell); additional centers will be enrolled.

REFERENCES

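### The significance level is printed as 0.05% (0.0005), which cannot give 83 per group at 90% power; two-sided 0.05 reproduces 83, so a stray percent sign is the likely cause

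*Combined protocol and SAP*

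**What the plan says.** Everything relevant is in the Statistical Procedures section of the combined protocol and SAP.

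- **Level, power and size:** "For a power of 90% and an alpha of 0.05%, this requires 83 subjects per group". Sidedness is not stated.
- **Effect:** "we determined that an absolute 25% decrease in PDPH would be clinically significant (i.e., 66% - 40"%). The control rate comes from the centre's internal quality data, put at about 66%.
- **Comparisons:** the figure of 83 applies to each of two separate contrasts, "2 epidural groups compared to each other, 2 spinal groups compared to each other".
- **Recruitment:** "We therefore aim to recruit 100 subjects per group (for a total of 400 across all centers"), to allow for a loss of 10 to 15%.
- **Analysis:** categorical outcomes, including presence or absence of headache, "will be analyzed using Chi-square analysis". This sentence gives no level and no sidedness.

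No other section states a significance level. No multiplicity adjustment, or any other reason for a level as strict as 0.0005, is given.

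**The concern.** An alpha of 0.05% is 0.0005, one hundredth of the conventional 5%. With a 26-point difference and 90% power, 83 per group is about what a 5% test needs and far too few for a test at 0.0005. The level and the sample size therefore cannot both be right.

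Two things are at stake. First, the sample size cannot be reproduced from the inputs printed beside it. Second, this sentence is the only place where a reader can find the threshold for the primary outcome. A result with p = 0.01 would be significant under the evident intention and not significant under the text, so an analysis reported at 0.05 would not match the protocol as written.

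**Working it through.** **Inputs** (all from Statistical Procedures): control rate p1 = 0.66; treatment rate p2 = 0.40 as printed, or 0.41 if the 25-point decrease is taken literally; power 90%; 83 per group; loss of 10 to 15%. Equal allocation follows from 100 per group. Sidedness is not given, so both were tried.

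**Formulas.** With p̄ = (p1 + p2)/2 and d = p1 − p2, the pooled normal approximation is

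n = [z_α √(2p̄(1−p̄)) + z_β √(p1(1−p1) + p2(1−p2))]² / d²

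and the continuity-corrected size is

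n_c = (n/4) × [1 + √(1 + 4/(n d))]².

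For 66% vs 40%, √(2p̄(1−p̄)) = 0.7058 and √(p1(1−p1) + p2(1−p2)) = 0.6815. For 90% power, z_β = 1.2816.

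**Step 1: reproduce 83.** At two-sided 0.05, z_α = 1.960:

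- n = (1.960 × 0.7058 + 1.2816 × 0.6815)² / 0.26² = 2.2568² / 0.0676 = 75.3, so 76.
- n_c = (75.34/4) × [1 + √(1 + 4/(75.34 × 0.26))]² = 18.835 × 2.0974² = 82.9, so **83**.

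For 66% vs 41%, the uncorrected formula gives 81.6, so 82, and the corrected one 89.4, so 90.

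**Step 2: use the printed level.** At two-sided 0.0005, z_α = 3.4808:

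- n = (3.4808 × 0.7058 + 1.2816 × 0.6815)² / 0.0676 = 3.3302² / 0.0676 = 164.05, so 165.

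Subjects per group for 90% power at 0.0005:

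| Rates | Sides | Unpooled | Pooled | Pooled, corrected |
|---|---|---|---|---|
| 66% vs 40% | two | 156 | 165 | 172 |
| 66% vs 40% | one | 144 | 152 | 159 |
| 66% vs 41% | two | 170 | 178 | 186 |
| 66% vs 41% | one | 156 | 164 | 172 |

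The range is 144 to 186. Even with power lowered to 80%, the smallest value is 118 (one-sided, unpooled, 66% vs 40%).

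**Step 3: which level does 83 imply?** Solving for the two-sided alpha that gives 90% power at 83 per group yields 0.0496 (66% vs 40%, corrected) or 0.0468 (66% vs 41%, uncorrected). One-sided 0.05 does not fit: 62 uncorrected and 69 corrected for 66% vs 40%, and 67 and 75 for 66% vs 41%.

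**Step 4: power.** Power = Φ{[d√n − z_α √(2p̄(1−p̄))] / √(p1(1−p1) + p2(1−p2))}. For 83 per group, 66% vs 40% and two-sided 0.0005, this is Φ[(2.3687 − 2.4568)/0.6815] = Φ(−0.129) = 44.9%. All figures below are two-sided and uncorrected:

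| Per group | Alpha | 66% vs 40% | 66% vs 41% |
|---|---|---|---|
| 83 | 0.05 | 92.6% | 90.5% |
| 83 | 0.0005 | 44.9% | 39.7% |
| 85 | 0.0005 | 46.5% | 41.3% |
| 90 | 0.0005 | 50.6% | 45.1% |
| 100 | 0.0005 | 58.3% | 52.6% |

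With continuity correction at 0.05, 83 per group gives 90.1% for 66% vs 40%. The rows for 85 and 90 are the evaluable numbers left from 100 after a loss of 15% or 10%.

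**Step 5: recruitment target.** 83/0.90 = 92.2, so 93; 83/0.85 = 97.6, so 98. Both are within 100 per group.

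**Step 6: could 0.0005 be deliberate?** A Bonferroni split over the two planned contrasts would give 0.05/2 = 0.025. Reaching 0.0005 that way would take 0.05/0.0005 = 100 comparisons. Nothing in the document points to such a scheme.

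**The case against.** The strongest reply is that this is a typographical slip that any statistician would read through. The adjacent figures point to 5%, no enrolment target or procedure depends on the correction, and no decision rule at 0.0005 exists for an analysis at 0.05 to breach. On that view the low power figures describe a trial that nobody intends to run. Most of this is fair. The power figures show only that the printed inputs conflict; they do not describe the expected performance of the trial. But it remains true that the sole statement of the threshold is wrong and that no second statement corrects it.

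A second objection also has force. The match to 83 depends on the formula. The document mentions no continuity correction and mixes a 25-point decrease with 66% minus 40%, which is 26 points. At two-sided 0.05, 66% vs 40% gives 76 without correction. The exact match was found by trying variants, and 66% vs 41% without correction comes within one subject. So the derivation of 83 is an inference that the sponsor should confirm, as is the two-sided reading, since one-sided 0.025 gives identical numbers. Neither point touches the main conclusion, because every variant at 0.0005 lies far above 83.

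**Conclusion.** The concern holds. The printed alpha is inconsistent with the sample size and power in the same sentence, under every formula, sidedness and rate pair tried. It is 100 times smaller than the level that reproduces 83, and the most plausible cause is a stray percent sign.

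This is a reporting error that should be fixed and not a design failure: at two-sided 0.05 the planned size delivers the stated 90% power, and 100 per group covers the assumed losses. The incompatibility rests only on the printed rates and power and on equal allocation. That the intended level is two-sided 0.05, and that 83 came from 66% vs 40% with continuity correction, are the best-fitting readings but are not stated in the document.

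**What to change.** In Statistical Procedures, replace the alpha of 0.05% with a two-sided alpha of 0.05 (5%), once the sponsor has confirmed that the test is two-sided. In the same sentence, give the basis of 83. If the sponsor confirms it, this is 66% vs 40% with continuity correction. If the intended contrast was 66% vs 41% without correction, the formula gives 82, and 83 per group has 90.5% power.

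The cost is one corrected figure and one clarifying phrase. Sample size, recruitment target and trial conduct do not change.

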Two Dose Neuraxial Morphine for Prevention of Postdural Puncture Headache

NCT02473276

IRB approval date: 05/12/2023

RESEARCH AIMS & ABSTRACTS

Research Question(s)/Hypothesis(es): This study aims to determine the efficacy of neuraxial (either epidural or intrathecal) preservative-free morphine to prevent headache after accidental dural puncture in parturients.

Our hypothesis is that 2 doses of neuraxial morphine (epidural or intrathecal) will be superior to placebo in reducing the incidence of postdural puncture headache.

Scientific Abstract: Neuraxial analgesia (most commonly continuous epidural or combined spinal epidural) is the most effective modality available for pain relief during labor. Accidental dural puncture (ADP) with a large bore epidural needle and the resulting post-dural puncture headache (PDPH) is one of the most significant sources of anesthesia-related morbidity in parturients. The incidence of ADP in this population is between 0.04 and 6% (most common cited is ~ 1%), and PDPH occurs in up to 80% of patients with an ADP. For many patients, the headache is debilitating, interfering with the ability to care for a new infant, and may be associated with other unpleasant symptoms, including diplopia, tinnitus, hypoacusis, photophobia, nausea, and dizziness. In the most severe cases, subdural hematoma can occur. Epidural blood patch is the gold standard for treatment of PDPH, and although almost always effective, can result in another ADP, as well as low back pain and lower extremity pain. For this reason, effective measures to prevent PDPH when ADP occurs would be highly valuable. One small study by Al-metwalli, et al. in which 50 women were randomly allocated to receive 2 epidural injections of morphine or saline, demonstrated a beneficial effect of epidural morphine in decreasing the incidence of PDPH. This study aims to determine the efficacy of 2 doses of neuraxial (either epidural or intrathecal) preservative-free morphine (PFM) to prevent headache after ADP in parturients.

Lay Abstract: Epidural or combined spinal epidural analgesia (pain relief) is the most effective modality available for the treatment of pain during labor. The most frequent, bothersome complication of performing these procedures is accidental dural puncture (ADP) with the epidural needle, commonly called a “wet tap.” The dura mater is the membrane that surrounds the fluid that cushions and bathes the brain and spinal cord. If the dura mater is

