One small study by Al-metwalli, et al. (4) in which 50 women were randomly allocated to receive epidural injections of morphine or saline, demonstrated a beneficial effect of epidural morphine in decreasing the incidence of PDPH. Interestingly, epidural morphine is often administered for post-operative analgesia after cesarean delivery, and in patients who experience ADP, cesarean delivery is associated with a lower incidence of PDPH than vaginal delivery (5). This study aims to determine the efficacy of neuraxial (either epidural or intrathecal) preservative-free morphine (PFM) to prevent headache after ADP in parturients.

Study Design: This will be a prospective, randomized, double blind clinical trial. Subjects will be postpartum ASA I and II women aged 18 years and older, who are known to have had ADP with an epidural needle during placement of neuraxial labor analgesia, and have either an intrathecal catheter or epidural catheter. Patients will be randomized to either receive PFM or placebo (sterile normal saline). For patients with an epidural catheter, the group “EPID PFM” will receive 3 mg (6 mL) of PFM, followed by 3 mL of sterile normal saline (NS) to be administered through the epidural catheter. The placebo group, “EPID NS”, will receive 6 mL of NS, followed by another 3mL of NS via the epidural catheter. For patients with an epidural catheter, the group “EPID PFM” will receive 3 mg (6 mL) of PFM, followed by 3 mL of sterile normal saline (NS) to be administered through the epidural catheter. The placebo group, “EPID NS”, will receive 6 mL of NS, followed by another 3mL of NS via the epidural catheter. For patients with an intrathecal catheter, the group, “IT PFM” will receive 200 micrograms (mcg)

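### Alpha is printed as 0.05% although the sample size rests on 5%, and the single hypothesis covering both routes has no analysis of its own beside the two within-route comparisons

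*Combined protocol and SAP*

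**What the plan says.** All references are to the combined protocol and SAP.

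- **Research Question(s)/Hypothesis(es)** gives one hypothesis for both routes: "Our hypothesis is that 2 doses of neuraxial morphine (epidural or intrathecal) will be superior to placebo". The end of Study Purpose and Rationale gives one aim in the same terms: "This study aims to determine the efficacy of neuraxial (either epidural or intrathecal) preservative-free morphine (PFM) to prevent headache after ADP in parturients".
- **Study Design** sets up four groups, morphine and saline for each catheter type, so each route has its own control.
- **Statistical Procedures** takes a control rate of about 66% and an absolute reduction of 25 points, illustrated as 66% to 40%. It then states: "For a power of 90% and an alpha of 0.05%, this requires 83 subjects per group". The comparisons being sized are "2 epidural groups compared to each other, 2 spinal groups compared to each other". The contrast between routes is set aside: "We are not specifically powering this for comparison of the spinal to the epidural groups". The target is 100 per group, "assuming 10- 15% of subjects may be lost".
- The analysis of the primary outcome is one sentence: "Categorical data (presence of absence of PDPH, need for EBP) will be analyzed using Chi-square analysis". It does not say which groups enter the test, and it gives no sidedness.

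**The concern.** There are two separate matters.

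1. **The threshold.** Alpha is the rule by which the primary result is judged. Read literally, 0.05% is 0.0005, a hundredth of the conventional 5%. An analyst who applied the printed figure would use a threshold for which the trial was not sized.

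2. **The link from tests to hypothesis.** The hypothesis speaks of neuraxial morphine as a whole, while the sizing describes two tests in different patients. The two comparisons can be identified from the sizing sentence, so the choice of groups is not the gap. What is absent is an analysis that addresses the overall hypothesis, and a statement of how far a positive result on one route may be carried. If one route is significant and the other is not, the wording of the conclusion would be settled after the results are known. A reader may also take the 90% power as the chance that the whole hypothesis is borne out on both routes, which it is not.

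**Working it through.** **Inputs (Statistical Procedures).** Control rate p1 = 0.66. Treated rate p2 = 0.41 (25 points) or 0.40 (the printed example); both are carried. Power is 90%, groups are equal, and there are 83 per group. With 100 recruited and 10 to 15% lost, 85 to 90 remain evaluable.

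**Assumptions.** Two-sided test; Pearson chi-square without continuity correction for the power figures; the two routes independent because they contain different patients.

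**Step 1: reproduce 83.** With p̄ the mean of p1 and p2, and d = p1 − p2:

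n = [z(α/2)·√(2p̄(1−p̄)) + z(β)·√(p1(1−p1)+p2(1−p2))]² / d²

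The continuity-corrected size is n/4·[1+√(1+4/(nd))]².

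- 66% vs 41%, α = 5%: [1.960×0.7054 + 1.2816×0.6829]² / 0.0625 = 2.2576² / 0.0625 = 81.6, so 82.
- 66% vs 40%, α = 5%: 2.2567² / 0.0676 = 75.3. Corrected: 75.3/4×[1+√(1+4/19.59)]² = 82.9, so 83.

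One-sided 2.5% uses the same z value and gives the same sizes.

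**Step 2: the printed alpha.** At two-sided 0.0005, z = 3.481.

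- 66% vs 40%, uncorrected: [3.481×0.7058 + 1.2816×0.6815]² / 0.0676 = 164.1, so 165.
- 66% vs 41%, corrected: 185.4, so 186.

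Power at 83 per group is Φ{[d√n − z·√(2p̄(1−p̄))] / √(p1(1−p1)+p2(1−p2))}. For 66% vs 41% this is Φ[(2.278 − 2.455)/0.683] = 0.397. Exact binomial enumeration gives 39.5% (66% vs 41%) and 44.6% (66% vs 40%).

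**Step 3: what the 90% covers.** Exact power of one route at 5%, and its square for both routes succeeding:

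| Evaluable per group | One route, 66 vs 41 | Both, 66 vs 41 | One route, 66 vs 40 | Both, 66 vs 40 |
|---|---|---|---|---|
| 83 | 0.907 | 0.82 | 0.927 | 0.86 |
| 85 | 0.917 | 0.84 | 0.936 | 0.88 |
| 90 | 0.920 | 0.85 | 0.938 | 0.88 |

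If both routes work, exactly one is significant with probability 2r(1−r), r being the one-route power. At 85 to 90 this runs from 2×0.938×0.062 = 0.12 to 2×0.917×0.083 = 0.15.

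**Step 4: a stratified test of the overall hypothesis.** Cochran-Mantel-Haenszel, morphine vs saline, stratified by route, 66% vs 41%, 400,000 simulated trials. Power is over 99% if both routes work. If only one works it is 65% at 83, 66% at 85 and 68% at 90 per group.

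**Step 5: error rates under each way of claiming.** With route-specific claims, each test keeps its own false-benefit risk of 2.5%. If a win on either route were allowed to confirm the general hypothesis, that risk would be 1 − (1 − 0.025)² = 4.9%.

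**The case against.** The strongest reply is that the plan already reads as two parallel trials: separate patients, separate saline controls, separate sizing, and an explicit statement that the routes are not being compared. On that reading each comparison keeps its own 5%, nothing is inflated, and what is missing is a sentence on how conclusions are worded. The alpha is a slip of notation that did not affect the calculation.

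Most of this stands. The route-specific reading is the natural one, and it is the one to keep. It does not dispose of the point, because the stated hypothesis is not route-specific and the printed threshold is wrong whatever its cause.

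Three stronger inferences are tempting, and the documents do not support them:

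- **That the false-positive risk is doubled.** This needs a rule that a win on either route confirms the general claim, and the plan adopts no such rule. The figure of 9.8% for any false significant result also counts results favouring saline, whereas the hypothesis is directional. The relevant comparison under that rule is 4.9% against 2.5%.
- **That a split result is about 90% likely if only one route works, and so is a flaw.** In that case one significant route is largely the correct answer. The figure is essentially the power of the working route.
- **That the trial is underpowered because of the 0.05%.** The size was evidently not calculated at that value.

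**Conclusion.** The point holds as a correction and a clarification. It is not a defect in the sample size. The printed alpha does not fit the plan's own 83 per group, which rests on 5% two-sided or, identically, 2.5% one-sided. The documents do not settle which was meant, though two-sided fits the planned chi-square. The overall hypothesis has no analysis assigned to it, and the 90% power describes one route at a time. The probability that both routes succeed is about 82 to 86% at 83 per group and 84 to 88% at 85 to 90.

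These figures assume a 66% control rate on both routes, the planned effect on both, an uncorrected chi-square test and independent routes. A multiplicity adjustment such as Hochberg would be called for only if a win on either route were to confirm the general claim.

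**What to change.** 1. Restate alpha as 5% and state the sidedness; two-sided fits the chi-square test. The 83 and 100 per group do not change.
2. Name the two within-route chi-square tests as the primary comparisons, and limit any positive claim to the route or routes whose own test succeeds. State that a win on one route does not establish the general neuraxial claim. No multiplicity adjustment is then needed.
3. State that the 90% power applies to each route separately, and give the probability that both succeed.
4. Add a Cochran-Mantel-Haenszel estimate and test of morphine vs saline, stratified by route, as the supportive analysis of the overall hypothesis. Say that it does not by itself show efficacy on each route: it would be significant in about 65 to 68% of trials in which one route has no effect.
5. If the sponsor prefers that a win on either route should confirm the general hypothesis, specify an adjustment such as Hochberg at 5%. For 66% vs 41% at 83 per group, power per route would fall from 90.7% to 90.1% if both routes work, and to 84.6% if only one does.

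The changes should be made before treatment codes are opened. The cost is one extra analysis and narrower claims after a single-route win. No further patients are needed.
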